1.7.6.4 Talimogene Laherparepvec

The most commonly reported adverse drug reactions (very common, $\geq 10\%$) in talimogene laherparepvec-treated patients were fatigue, chills, pyrexia, nausea, influenza-like illness, and injection site pain. Adverse events such as vomiting, diarrhea, constipation, myalgia, arthralgia, extremity pain, headache and abdominal pain, were also reported as very common.

Dose reductions with regards to changes in the concentrations of talimogene laherparepvec are not permitted. However, patients may require a reduction in the volume injected due to a disease response or due to local toxicity at the injection site.

Dose delays are allowable. If severe/grade 4 toxicities occur, talimogene laherparepvec administration should be delayed until the toxicity has resolved to at least a grade 1. Dosing of talimogene laherparepvec could also be delayed for active herpetic cutaneous or mucosal lesions, herpes labialis, antiviral therapy, or active dermatoses in the region of the injected tumors.

If talimogene laherparepvec treatment was delayed due to adverse events or other reasons by > 2 week, that dose will be deemed to have been missed and the subject will proceed to the next scheduled treatment visit.

If talimogene laherparepvec dosing is delayed by more than 4 weeks (approximately 6 weeks from the previous dose) due to adverse events that are related to talimogene laherparepvec, then treatment should be discontinued. If talimogene laherparepvec dosing is delayed by more than 4 weeks (approximately 6 weeks from the previous dose) for reasons other than treatment-related toxicity, the case must be reviewed by the sponsor of the investigator sponsored study (ISS) to determine if the subject can resume talimogene laherparepvec therapy.

If the subject requires corticosteroid dosing of > 10 mg prednisone daily (or equivalent) and/or other immunosuppressive medication for related toxicities, talimogene laherparepvec dosing must be held until the corticosteroid dose has decreased to < 10 mg prednisone daily (or equivalent) and the administration of the other immunosuppressive medication has discontinued.

1) Immune-mediated Adverse Events

Immune-mediated adverse events have been observed in subjects receiving talimogene laherparepvec. These included pauci-immune glomerulonephritis, vasculitis, and pneumonitis; however, immune-mediated adverse events can potentially involve any organ system.

Permanently discontinue talimogene laherparepvec if dosing is delayed by more than 4 weeks due to a Grade 2 or greater immune-mediated adverse event (with the exception of vitiligo), allergic reactions, or urticaria attributed to talimogene laherparepvec.

2) Plasmacytoma

Plasmacytoma has been observed with the administration of talimogene laherparepvec. Permanently discontinue talimogene laherparepvec if development of a plasmacytoma is observed.

3) Injection Site Reactions

Talimogene laherparepvec is administered by direct injection into cutaneous, subcutaneous, and nodal tumor masses. Injection site adverse events may occur, such as erythema, local skin discoloration, induration, warmth, and pain. Less frequently, injected cutaneous tumor masses may undergo necrosis, predisposing the subject to local and/or systemic infections. Similarly, injected pathologic lymph nodes may enlarge or become necrotic. Uncommonly, necrotic lymph nodes may be the site of persistent drainage that requires corrective measures. In clinical studies, adverse events of "injection site pain" and "injection site reaction" were very common, occurring in $\geq 10\%$ of talimogene laherparepvec-treated subjects. Most events of injection site pain and injection site reaction in subjects receiving talimogene laherparepvec were mild to moderate in severity. Subjects seronegative at baseline for HSV-1, when given an initial dose of talimogene laherparepvec at a concentration of 10^6 PFU/mL, do not appear to experience more exaggerated injection site reactions than those who are seropositive at baseline.

4) Cellulitis

Necrosis of cutaneous tumor masses and pathologic lymph nodes injected with talimogene laherparepvec may infrequently occur, predisposing to local/regional infection (i.e., cellulitis). In clinical studies to date, cellulitis was common, occurring in $\geq 1\%$ to $< 10\%$ of subjects treated with talimogene laherparepvec.

5) Flu-like Symptoms

Constitutional symptoms including chills, fatigue, headache, myalgia, and pyrexia may occur with talimogene laherparepvec. Collectively, this constellation of symptoms may be described as “flu-like symptoms”. In clinical studies to date, adverse events with the MedDRA preferred terms “chills”, “fatigue”, “headache”, “influenza like illness”, “myalgia”, and “pyrexia” were very common, occurring in $\geq 10\%$ of subjects treated with talimogene laherparepvec. Most of these events were mild to moderate in severity. Subjects seronegative at baseline for HSV-1, when given an initial dose of talimogene laherparepvec at a concentration of 10^6 PFU/mL, do not appear to experience more flu-like symptoms than those who are seropositive at baseline. These symptoms are self-limiting and resolve without sequelae.

1.7.7 Supportive Care Guidelines:

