Dose modifications will follow the guidelines below. In general, therapy will continue with grade 1 or tolerable grade 2 toxicities. Intolerable grade 2, grade 3, or grade 4 toxicities will result in holding therapy as follows:

1.7.6.1 Dose modification guidelines for talimogene laherparepvec:

Reductions

Dose reductions with regards to changes in the concentrations of talimogene laherparepvec are not permitted. However, patients may require a reduction in the volume injected due to a disease response or due to local toxicity at the injection site. However, if in the course of administration of talimogene laherparepvec the subject cannot tolerate the full dose due to an injection-related adverse event such as pain, the total volume given should be recorded, and the reason for intolerance should be documented as an adverse event.

1.7.6.2. Talimogene Laherparepvec Dosage Adjustments, Delays, Rules for Withholding or Restarting, Permanent Discontinuation:

If talimogene laherparepvec treatment was delayed by > 2 weeks, that dose will be deemed to have been missed and the subject will proceed to the next scheduled treatment visit. Dose reductions of talimogene laherparepvec is not permitted, other than a reduction in the volume injected due to a disease response. CTCAE 4.0 criteria listed in Table 7 are used to determine toxicity grades.

If a subject experience any of the following treatment-related toxicities, talimogene laherparepvec administration should be delayed until the toxicity has resolved to at least CTCAE grade 1 or baseline (Table 7):

- grade 2 or greater immune-mediated adverse events, with the exception of vitiligo.
- grade 2 or greater allergic reactions.
- any other grade 3 or greater hematologic or non-hematologic toxicity.

Table 7. CTCAE 4.0 Criteria:

Symptom	Grade 1	Grade 2	Grade 3	Grade 4
---------	---------	---------	---------	---------

Version Number: v10, March 23, 2023

Protocol Number: #091804

PI Name: [name]

Protocol Title: A Phase I Study of Talimogene
Laherparepvec and Panitumumab in Patients with
Locally Advanced Squamous Cell Carcinoma of the
Skin (SCCS)

26

RESERVED FOR IRB STAMP
DO NOT MODIFY THIS SPACE

RUTGERS | eIRB
APPROVED

IRB Form Version 12.18.2018

IRB ID:

2018002628

Approval Date:

4/12/2023

Expiration Date:

9/21/2023

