In one study [44], dermatologic toxicities occurred in 90% of patients and were severe (grade 3 and higher) in 15% of patients receiving panitumumab. The clinical manifestations included, but were not limited to acneiform dermatitis, pruritus, erythema, rash, skin exfoliation, paronychia, dry skin, and fissures. Monitor patients who develop dermatologic or soft tissue toxicities while receiving panitumumab for the development of inflammatory or infectious sequelae. Withhold or discontinue panitumumab for dermatologic or soft tissue toxicity associated with severe or life-threatening inflammatory or infectious complications. Patients should be advised to avoid sun exposure while receiving panitumumab.

In previous reports, the Common Terminology Criteria for Adverse Events (CTCAE) 4.0 (Table 7) have been used for EGFR-associated rash.

4) Interstitial Lung Disease (ILD)

ILD may be acute in onset and has been observed in 1.3 % of patients, and some cases have been fatal. If patients experience worsening of respiratory symptoms such as dyspnea, cough and fever, panitumumab should be interrupted and the patient should be promptly investigated. If ILD is confirmed, panitumumab should be discontinued and the patient treated appropriately.

5) Electrolyte Abnormalities

Progressively decreasing serum magnesium levels leading to severe (grade 3-4) hypomagnesemia occurred in up to 7% [45] of patients across clinical trials. Monitor patients for hypomagnesemia and hypocalcemia prior to initiating treatment with panitumumab, periodically during treatment, and for up to 8 weeks after the completion of treatment. Other electrolyte disturbances, including hypokalemia, have also been observed. Replete magnesium and other electrolytes as appropriate.

6) Infusion Reactions

In one study [44], 4% of patients receiving panitumumab experienced infusion reactions, and 1% of patients experienced severe infusion reactions (grade 3-4). Infusion reactions, manifesting as fevers, chills, dyspnea, bronchospasm, and hypotension, can occur following panitumumab administration. Table 9 and 10 show the grading criteria for infusion reactions and dose modifications for infusion reactions, respectively. Fatal infusion reactions occurred in post-marketing experience.

Table 9. Grading Infusion Reactions:

	Grade 1	Grade 2	Grade 3	Grade 4

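### Sections 1.7.6.2 and 1.7.6.4 give different triggers for delaying talimogene, so some grade 3 events and grade 2 immune-mediated or allergic events can be handled in two ways

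*Combined protocol and SAP*

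**What the plan says.** Three places in the protocol bear on holding talimogene. All are current text, not amendment history.

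- **Section 1.7.6 (introduction, both drugs).** After saying that therapy generally continues through grade 1 or tolerable grade 2 toxicity, it adds: "Intolerable grade 2, grade 3, or grade 4 toxicities will result in holding therapy as follows".
- **Section 1.7.6.2 (talimogene adjustments and delays).** The rule opens "If a subject experience any of the following treatment-related toxicities" and the instruction is that "talimogene laherparepvec administration should be delayed until the toxicity has resolved to at least CTCAE grade 1 or baseline". Three triggers are listed: "grade 2 or greater immune-mediated adverse events, with the exception of vitiligo", "grade 2 or greater allergic reactions" and "any other grade 3 or greater hematologic or non-hematologic toxicity".
- **Section 1.7.6.4 (a second section on talimogene).** It repeats rules on injected volume, missed doses, the 4-week limit and corticosteroids, and gives its own delay trigger: "If severe/grade 4 toxicities occur, talimogene laherparepvec administration should be delayed until the toxicity has resolved to at least a grade 1". The preceding sentence says only that delays are permitted. The section does not refer back to 1.7.6.2.

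**The concern.** Section 1.7.6.4 reads as a free-standing rule set. A site that consulted only that section could reasonably take its delay trigger as complete, and it is not the trigger in 1.7.6.2. Two sites with the same event could then act differently while each followed the protocol.

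The first stake is safety, because the rule decides whether a patient with ongoing toxicity is injected again. The second is interpretation. Under both sections a delay of more than 2 weeks turns the dose into a missed one, and a delay of more than 4 weeks for a talimogene-related event ends talimogene. The delay trigger therefore feeds into how much talimogene patients receive and how many stop. The trial is single-arm, with 30 patients from several institutions, so there is no concurrent control against which uneven handling would average out.

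**Working it through.** No formula or planned figure is involved. The check is a comparison of the two talimogene rules, followed by the events on which they part.

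| Element | 1.7.6.2 | 1.7.6.4 |
|---|---|---|
| General grade trigger | Grade 3 or greater | Severe/grade 4, not defined |
| Immune-mediated (not vitiligo) | Grade 2 or greater | No delay trigger stated |
| Allergic reaction | Grade 2 or greater | No delay trigger stated |
| Attribution | Treatment-related only | Not limited |
| Resume at | Grade 1 or baseline | At least grade 1 |
| Cross-reference | None to 1.7.6.4 | None to 1.7.6.2 |

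**Step 1: two readings of severe/grade 4.** If the slash means *that is*, the trigger is grade 4 and grade 3 is left out. If it means *or*, and severe covers grade 3, then grade 3 is included and the grade 4 label adds nothing. The protocol does not say which is meant.

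**Step 2: events one at a time.**

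- *Treatment-related grade 3, neither immune-mediated nor allergic.* 1.7.6.2 says delay. 1.7.6.4 says delay on the wider reading; on the narrower reading it only permits delay.
- *Treatment-related grade 2 immune-mediated (not vitiligo) or allergic event.* 1.7.6.2 says delay. The 1.7.6.4 delay sentence does not reach it on either reading.
- *Grade 4 event judged unrelated.* 1.7.6.4 says delay. The 1.7.6.2 list does not apply.
- *Event that has returned to a baseline above grade 1.* 1.7.6.2 allows dosing to resume. 1.7.6.4 does not.

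The first case depends on the reading. The other three differ on both readings.

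**Step 3: remove events for which delay is moot.** Section 1.7.6.2 permanently discontinues talimogene when a DLT occurs in the evaluation period. Section 1.7.9 counts most grade 3 or greater events within four weeks of study treatment as DLTs, so those drop out. What remains at grade 3 is the set of events excluded from the DLT definition (for example grade 3 rash under 1.7.9, and grade 3 fatigue, which 1.7.9.1 does not class as a talimogene DLT) and events outside the DLT window. Section 1.7.6.4 itself lists fatigue among the most common talimogene reactions, so this set need not be empty.

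**Step 4: consequence per patient.** Take the three initial combination cycles to start on days 22, 36 and 50 (22 + 14 = 36; 36 + 14 = 50). One delay long enough to count as a missed dose then removes 1 of 3 talimogene doses at the higher concentration before the day 64 assessment.

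**The case against.** The strongest reply is that nothing here is a flat contradiction. Section 1.7.6.4 never tells a site to keep dosing at grade 3, and a site that delays under 1.7.6.2 breaches nothing in it. Section 1.7.6.3 also describes dermatologic toxicities that "were severe (grade 3 and higher) in 15% of patients receiving panitumumab". On that usage, severe/grade 4 would take in grade 3 and the grade 3 difference would disappear.

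Part of this stands: the grade 3 difference is an ambiguity, not a proven conflict. But the usage in 1.7.6.3 comes from a description of earlier panitumumab data and is not a definition for the protocol. Being told to delay is also not the same instruction as being permitted to. The wider reading leaves the missing grade 2 triggers, the attribution limit and the resolution level untouched.

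On the grade 2 triggers there is a partial answer. Later in 1.7.6.4, the permanent-discontinuation rule for delays beyond 4 weeks mentions grade 2 or greater immune-mediated events and allergic reactions. That presupposes such events can delay dosing, but it does not instruct the delay.

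Three stronger readings are tempting and are not supported:

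- *That every non-immune, non-allergic grade 3 event is affected.* Those that are DLTs in the evaluation period already lead to permanent discontinuation.
- *That toxicity counts or the stopping rule depend on the section followed.* The DLT definitions in 1.7.9 and 1.7.9.1 do not use a talimogene dose delay as a criterion. The posterior-probability rule in 6.1.2 counts hospitalizations and delayed or cancelled surgery, not delayed injections. An indirect effect through later exposure is conceivable but not shown.
- *That the introduction to 1.7.6 sets a third competing threshold.* It speaks in general terms for both drugs and hands over to the subsections.

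**Conclusion.** The point holds as an internal inconsistency in a dosing-safety rule. Sections 1.7.6.2 and 1.7.6.4 differ on the grade 2 triggers, attribution and resolution level whatever severe/grade 4 means, and on grade 3 if it means grade 4 only. The events exposed are grade 2 immune-mediated (not vitiligo) or allergic events, grade 3 events that have not already ended talimogene as DLTs, unrelated grade 4 events, and events that return to a baseline above grade 1.

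The effect runs through delays to missed doses and withdrawals. The documents give no expected frequency for these events, so no number of patients can be stated. Nothing in the primary response analysis, the two-stage boundaries or the safety stopping boundary is shown to change. The conclusion assumes that sites may act on either section, since both are in force and neither is given precedence. It makes no judgement on which trigger is right.

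**What to change.** Reconcile 1.7.6.2 and 1.7.6.4 into one talimogene delay criterion, stated once, with the other section and the introduction to 1.7.6 pointing to it. The single statement should settle:

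- the grade trigger for each class of event, with severe/grade 4 either defined or removed;
- whether the rule is limited to treatment-related events, and if so related to which drug;
- the level at which dosing may resume, including how baseline is treated.

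The sponsor decides the content of each item. The cost is a wording amendment and a notice to sites. Sample size, endpoints and analysis are unchanged.

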1.7.7.1. Panitumumab

Anti-emetics: Low emetogenicity. Follow local anti-emetic policy.

Supportive medications: Hydrocortisone, chlorphenamine and paracetamol can be given for chills/fever/rigor during the infusion, if required.

Treatment of dermatologic reactions may include a moisturizer, sun screen (SPF >15 UVA/UVB), topical steroids and/or oral antibiotics. Advise patients to wear sunscreen, a hat and limit sun exposure. Further recommendations are below:

- 1) Antibiotics: The benefit of routine antibiotics in uncomplicated (uninfected) rash is unclear. Some clinicians have used oral minocycline (Minocin), mupirocin (Bactroban), or topical clindamycin (Cleocin). Rash complicated by cellulitis should be treated with appropriate antibiotics based on clinical judgment or microbial sensitivity analysis.
- 2) Anti-histamines: Diphenhydramine (Benadryl) or hydroxyzine (Atarax) may be helpful to control itching.
- 3) Topical Steroids: The benefit of topical steroids is unclear. Topical hydrocortisone cream will be provided for pruritus not relieved with anti-histamine use.
- 4) Retinoids: There are no data to support the use of retinoids. Use is not advised.
- 5) Benzoyl Peroxide: Benzoyl peroxide should NOT be used as it may aggravate rash.
- 6) Makeup: Makeup may be used to cover the rash, but it should not make the rash worse. Dermatologist-approved makeup should be used (e.g., Dermablend). Makeup should be removed with a skin-friendly liquid cleanser (e.g., Neutrogena, Dove, Ivory Skin Cleansing Liqui-Gel).
- 7) Moisturizers: Emollients should be used to prevent and alleviate skin dryness (e.g., Neutrogena Norwegian Formula Hand Cream, Vaseline Intensive Care Advanced Healing Lotion).
- 8) Over-the-Counter Medications: Over-the-counter acne vulgaris medications (e.g., benzoyl peroxide) should not be used and could make the rash worse.

1.7.7.2 Talimogene Laherparepvec

Throughout the study, investigators may prescribe supportive care medications as needed for

Version Number: v10, March 23, 2023

Protocol Number: #091804

PI Name: [name]

Protocol Title: A Phase I Study of Talimogene Laherparepvec and Panitumumab in Patients with Locally Advanced Squamous Cell Carcinoma of the Skin (SCCS)

RESERVED FOR IRB STAMP
 DO NOT MODIFY THIS SPACE

RUTGERS | eIRB
 APPROVED

IRB Form Version 12.18.2018

IRB ID: 1402018002628

Approval Date:

4/12/2023

Expiration Date:

9/21/2023

treatment of talimogene laherparepvec toxicities. These include but are not limited to treatment for peri-injectional fever and chills, for which antipyretics and antihistamines (i.e. acetaminophen, indomethacin and diphenhydramine) may be prescribed.

1.7.8 Important Identified and Potential Risks

1.7.8.1 Panitumumab

Consult the current Investigator's Brochure (IB) for the full information on the Identified and Potential Risks of panitumumab and Adverse Drug Reactions (ADRs).

1.7.8.1 Talimogene laherparepvec

Consult the current Investigator's Brochure (IB) for the full information on the Identified and Potential Risks of talimogene laherparepvec and Adverse Drug Reactions (ADRs).

1.7.9 Dose-Limiting Toxicity

Dose-limiting toxicity is defined as any occurrence of CTCAE grade 3 or greater adverse event in four weeks following the administration of the study products except grade 3 laboratory values not deemed clinically significant, grade 3 fatigue which resolves within 72 h of holding or modifying protocol therapy and grade 3 rash, as the latter is an already known potential side effect of panitumumab.

1.7.9.1 Talimogene laherparepvec DLTs

For Talimogene laherparepvec, the following events should also be considered as DLTs.

- Herpetic events:
 - Serious herpetic events such as herpetic encephalitis, encephalomyelitis or disseminated herpetic infection.
 - Any herpetic events confirmed due to talimogene laherparepvec that require treatment with acyclovir or similar anti-viral agent. Talimogene laherparepvec treatment should be suspended if treatment is required with systemic acyclovir or other anti-virals. If ongoing anti-viral treatment is required, talimogene laherparepvec treatment should be permanently discontinued.
- Any grade plasmacytoma at or near the injection site or evidence of impaired wound healing at the injection site.
- Grade 3 non-hematologic toxicity lasting > 3 days despite optimal supportive care;
- Grade 3 fatigue will not be classified as DLT, irrespective of duration.
- Any Grade 3 or higher non-hematologic laboratory value if the abnormality fails to respond to medical intervention, or leads to hospitalization, or persists for > 1 week unless deemed not clinically important per both investigator and sponsor.
- Any other intolerable toxicity leading to permanent discontinuation of talimogene laherparepvec.

1.7.10 Drug/Device Accountability and Storage Methods

1.7.9.1 Drug Products Storage and Security

The investigator or an approved representative (e.g., pharmacist) will ensure that all drugs and any other study related material is stored in a secured area, under recommended temperature monitored storage conditions, in accordance with applicable regulatory requirements.

To prevent theft or diversion, the drugs will be stored in a securely locked, substantially constructed cabinet or enclosure appropriate for a drug. Any actual or suspected theft or diversion must be reported immediately.

Version Number: v10, March 23, 2023

Protocol Number: #091804

PI Name: [name]

Protocol Title: A Phase I Study of Talimogene
Laherparepvec and Panitumumab in Patients with
Locally Advanced Squamous Cell Carcinoma of the
Skin (SCCS)

34

RESERVED FOR IRB STAMP
DO NOT MODIFY THIS SPACE

RUTGERS | eIRB
APPROVED

IRB Form Version 12.18.2018

IRB ID:

18002628

Approval Date:

4/12/2023

Expiration Date:

9/21/2023

